7.8. Follow up

Participants will be seen post procedure prior to discharge to exclude any adverse events. This will represent the end of the study. No further research follow up is required for most but routine clinical follow up will take place including participant access to arrhythmia specialist nurse practitioners. Participants undergoing AcQMap guided ablation and cardiac MRI will undergo a repeat cardiac MRI 3-6 months after the procedure. This will be planned wherever possible to take place at the same time as attending for routine clinical follow up after the procedure.

7.9. Discontinuation/Withdrawal of Participants from Study

Each participant has the right to withdraw from the trial at any time. In addition, the Investigator may discontinue a participant from the trial at any time if the Investigator considers it necessary for any reason including:

- Pregnancy
- Ineligibility (either arising during the trial or retrospectively having been overlooked at screening)
- Significant protocol deviation
- An adverse event which requires discontinuation of the catheter ablation or results in inability to continue to comply with trial procedures
- Withdrawal of Consent

If a patient is withdrawn or voluntarily withdraws from the trial prior to the study procedure then all study data collected will be excluded and they will be replaced in the study. If any event during the procedure results in necessary deviation from the study protocol on grounds of clinical necessity then any data collected up to that point will be analysed. It may be required to recruit additional patients if this occurs depending on the extent to which data had been collected. This is at the discretion of the chief investigator.

The reason for withdrawal will be recorded in the CRF.

7.10. Definition of End of Study

The end of the study is defined as the end of the study procedure for the last study participant.

8. SAFETY REPORTING

8.1. Definition of Serious Adverse Events

A serious adverse event is any untoward medical occurrence that:

- results in death
- is life-threatening
- requires inpatient hospitalisation or prolongation of existing hospitalisation
- results in persistent or significant disability/incapacity
- consists of a congenital anomaly or birth defect.

Other 'important medical events' may also be considered serious if they jeopardise the participant or require an intervention to prevent one of the above consequences.

NOTE: The term "life-threatening" in the definition of "serious" refers to an event in which the participant was at risk of death at the time of the event; it does not refer to an event which hypothetically might have caused death if it were more severe.

8.2. Reporting Procedures for Serious Adverse Events

A serious adverse event (SAE) occurring to a participant should be reported to the REC that gave a favourable opinion of the study where in the opinion of the Chief Investigator the event was 'related' (resulted from administration of any of the research procedures) and 'unexpected' in relation to those procedures. Reports of related and unexpected SAEs should be submitted within 15 working days of the Chief Investigator becoming aware of the event, using the HRA report of serious adverse event form (see HRA website).

9. STATISTICS AND ANALYSIS

9.1. Description of Statistical Methods

This is a mechanistic study exploring a change in electrogram morphology. This will be expressed as a proportion of signals recorded within each amplitude bracket. Statistical comparisons using the chi-square tests of 2 proportions will be made to look for significant differences at long and short cycle length.

In the sub-study comparing voltage mapping methods, simple statistical analysis will be used to compare voltage amplitudes obtained by each method in sinus rhythm and in AF. Means will be compared using independent sample t-test.

Retrospective analyses may be conducted to explore trends in electrophysiological mechanisms identified and their relation to demographic, anatomical, or clinical features recorded and in line with secondary outcome measures.

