3. BACKGROUND AND RATIONALE

Atrial fibrillation is a common condition resulting in significant morbidity and mortality. Catheter ablation based around a strategy of pulmonary vein isolation is increasingly used to maintain sinus rhythm.(1) However, particularly in patients with persistent atrial fibrillation, efficacy is limited with single-procedure success rates of <50%.(2-5) Although a number of techniques targeting non-pulmonary vein mechanisms have been explored, none has demonstrated superior efficacy in randomised controlled trials.(5) This is in large part due to a lack of understanding of AF mechanisms or subgroups of AF phenotypes and the contribution of identified conduction patterns to arrhythmia maintenance and propagation.

Assessment of atrial substrate is often performed through electroanatomical voltage mapping (EAVM) using multipolar or bipolar catheters. Regions of low voltage amplitude, used as a surrogate for fibrosis, predict worse outcomes following catheter ablation.(6-8) Prior studies have varied in the technology used to conduct EAVM and how low voltage areas are defined. They have largely focused on regions with bipolar amplitude <0.5mV with normal being defined as >1.1 or 1.3mV.(9, 10) The significance of regions with amplitude between these values (intermediate voltage) is poorly understood but there is some evidence that highly fractionated electrograms are seen in these areas(9, 10) which correlate with patchy enhancement rather than dense fibrosis on late gadolinium enhanced cardiac MRI (LGE-MRI). The presence of intermediate and low voltage areas is associated with AF recurrence following pulmonary vein isolation (PVI).(11, 12) Interestingly, a significant proportion of patients undergoing catheter ablation for persistent AF do not demonstrate regions of low voltage implying that it is not purely these regions that are important for AF maintenance.(7, 13) There also appears to be fairly poor correlation between AF duration and the presence of fibrosis, with some patients with longstanding AF demonstrating scar-free atria, whilst some with only brief episodes have highly scarred atria.(13, 14)

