4. OBJECTIVES AND OUTCOME MEASURES

Objectives	Outcome Measures	Timepoint(s) of evaluation of this outcome measure (if applicable)
Primary To define the normal range of voltage amplitude identified using the Abbott EnSite Advisor HD grid (SE) catheter and HD wave solution and response to pacing cycle lengths using a control group with normal	Mean and distribution of left atrial voltage amplitude across the whole chamber and by segments with lower limit of normal defined as the upper 95% value within the segment with the lowest mean amplitude at long pacing cycle length	During ablation procedure

left atria		
Secondary: To characterise the left atrial electrophysiological substrate using electroanatomical voltage and activation mapping using the Abbott EnSite Advisor HD grid (SE) catheter during pacing using a basic cycle length and a single closely coupled extra-stimulus in a cohort of patients undergoing catheter ablation for atrial fibrillation.	A change in electrogram morphology from normal to abnormal (defined as ≥3 deflections lasting ≥50ms) between long and short pacing cycle length in regions of low (<0.5mV), intermediate (0.5-lower limit of normal defined from control group) and normal (defined from control group results) voltage amplitude.	During ablation procedure
	Difference in single vector conduction velocity at long and short cycle lengths in regions of low, intermediate and normal voltage.	During ablation procedure
In a subgroup of 20 patients: To compare electroanatomic voltage mapping (EAVM) performed with a bipolar contact force guided ablation catheter to the Abbott HD grid using orthogonal wave analysis in sinus rhythm.	1. Difference in voltage amplitude by each method in sinus rhythm 2. Surface area and proportion of points of scar (<0.05mV), low voltage (0.05-0.4mV), intermediate voltage and normal voltage (voltage cut-offs defined from control group).	During ablation procedure
In a subgroup of 10 patients: Correlate findings of high density contact mapping with AF propagation patterns using the AcQMap combined imaging and electrophysiological mapping system.	Correlate electrogram amplitude and morphology with regions of uniform, irregular, slow or rotational activation patterns during AF.	During ablation procedure

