9.3. Analysis of Outcome Measures

Control group:

All electrogram samples will be analysed at baseline (long) cycle length and classified as normal or abnormal (see above definitions in section 4). The same sampling points will then be analysed at short cycle length and classified in the same way. The proportion of electrograms changing from normal to abnormal will be recorded as will the change in electrogram amplitude and duration.

The whole chamber mean, median and distribution of voltage amplitude at long cycle length will be analysed. This will also be done for each atrial segment. The segment with the lowest mean amplitude will be identified and the cut-off for the value representing the upper 95% of recordings in that segment calculated. This will be used as the value representing the lower limit of normal for subsequent study analyses.

All participants:

All electrogram samples will be analysed at baseline (long) cycle length and classified as normal or abnormal (see above definitions in section 4). The same sampling points will then be analysed at short cycle length and classified in the same way. The proportion of electrograms classified as normal and abnormal at each cycle length will be calculated for the full sample set and according to baseline electrogram amplitude (<0.5mV, 0.5-lower limit of normal, and >lower limit of normal)(lower limit of normal defined above from analysis of the control group).

For each participant, conduction velocities will be analysed in regions of different baseline electrogram amplitude at both long and short cycle length. This will be done using the Turbomap feature in Precision to create an activation map (specified as measuring on maximum negative dV/dt). Conduction velocity will be calculated as a mean of 5 measurements using the difference in activation times between 2 points in a straight line at set distance through the region of least isochronal crowding. This will be done in regions of low, intermediate and preserved voltage at long and short cycle length.

The outcome measures will be assessed in all patients in whom the study procedure was performed.

Voltage mapping subgroup:

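### The normal-to-abnormal morphology change is expressed over all signals in a voltage bracket, so brackets or regions that differ in baseline fractionation cannot be compared on rate-sensitivity, and conversions cannot be told apart from reversions

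*Combined protocol and SAP*

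**What the plan says.** Section 4 defines the secondary morphology outcome as "A change in electrogram morphology from normal to abnormal (defined as ≥3 deflections lasting ≥50ms) between long and short pacing cycle length", to be examined in low, intermediate and normal voltage. Section 9.1 sets the scale for the change: "This will be expressed as a proportion of signals recorded within each amplitude bracket".

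Section 9.3, for all participants, starts from every signal: "All electrogram samples will be analysed at baseline (long) cycle length and classified as normal or abnormal". It then pairs them: "The same sampling points will then be analysed at short cycle length and classified in the same way". The quantity to be reported is not a transition, however: "The proportion of electrograms classified as normal and abnormal at each cycle length will be calculated for the full sample set and according to baseline" amplitude. A transition proportion is named only for the control group ("The proportion of electrograms changing from normal to abnormal will be recorded as will the change in electrogram amplitude and duration"), and its denominator is not stated.

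Two comparisons between tissue types depend on how this outcome is scaled. The last paragraph of Section 3 hypothesises that, as cycle length shortens, electrograms broaden more in intermediate than in preserved voltage. The AcQMap part of Section 9.3 compares operator-identified regions with the rest of the atria on, among other things, the proportional change in morphology. On intermediate-voltage areas, Section 3 also reports that "there is some evidence that highly fractionated electrograms are seen in these areas".

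**The concern.** Only a signal that is normal at long cycle length can change from normal to abnormal. If the denominator also holds signals that are already abnormal, the figure mixes two things: how readily normal signals convert, and how many signals were available to convert. Two brackets with the same conversion risk will then show different figures whenever their baseline abnormal shares differ. This happens even if every electrogram is classified correctly.

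What is at stake is the reading of the Section 3 hypothesis. The background suggests more baseline fractionation in intermediate voltage, the tissue that is expected to respond most to a short coupling interval. On the all-signals scale its response may be diluted relative to preserved voltage. Section 3 presents the results as pilot data for larger studies, so a diluted contrast could carry forward.

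**Working it through.** The plan states no baseline abnormal rate, conversion rate, effect size or power for this outcome, so there is no figure of its own to reproduce. The check is algebra, followed by illustrations on assumed rates.

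**Inputs, for one bracket**
- b: share of signals abnormal at long cycle length (assumed, 5% to 50%).
- q: probability that a baseline-normal signal becomes abnormal at short cycle length (assumed, 10% to 30%).
- r: probability that a baseline-abnormal signal becomes normal (assumed, 0 or 10%).

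**Formulas**
- Conversions over all signals: (1-b)q.
- Net change in the abnormal proportion, short minus long: (1-b)q - br.
- Conversions over signals normal at long cycle length: q, whatever b is.

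**Equal conversion risk, unequal baseline (r = 0)**
- q = 20%, b = 10% versus 40%: 0.90 × 0.20 = 18% versus 0.60 × 0.20 = 12%.
- q = 20%, b = 5% versus 20%: 0.95 × 0.20 = 19% versus 0.80 × 0.20 = 16%.
- q = 10%, b = 5% versus 40%: 9.5% versus 6%.
- q = 30%, b = 5% versus 40%: 28.5% versus 18%.

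In each pair the at-risk proportion is the same in both brackets.

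**How much higher the true risk must be just to look equal.** The factor is (1 - b_ref)/(1 - b). With b_ref = 5% it is 0.95/0.80 = 1.19 at b = 20%, 0.95/0.60 = 1.58 at b = 40% and 0.95/0.50 = 1.90 at b = 50%.

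**The order can reverse.** Take 300 signals in each bracket.
- Reference bracket, b = 5%, q = 20%: 285 at risk and 57 conversions, so 57/300 = 19%.
- Other bracket, b = 40%, q = 30%: 180 at risk and 54 conversions, so 54/300 = 18%.

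On the at-risk scale these are 20% and 30%.

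**Reversions.** With q = 20% and r = 10%, the net change is 0.19 - 0.005 = 18.5% at b = 5%, and 0.12 - 0.04 = 8% at b = 40%. Dividing the net change by (1-b) does not repair this: 0.08/0.60 = 13.3%, not 20%.

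**What the planned proportions can identify.** They give b and the abnormal proportion at short cycle length, b + (1-b)q - br. That is one equation in two unknowns. With b = 40% and 48% abnormal at short cycle length, q = 20% with r = 10% fits (0.40 + 0.12 - 0.04), and so does q = 13.3% with r = 0 (0.40 + 0.08). Only the paired table separates them.

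**The case against.** The strongest reply is that the planned test does not make the comparison at issue. Section 9.1 specifies chi-square tests between long and short cycle length, and Section 9.2 frames the hypothesis as morphology becoming abnormal at shorter cycle length. For that comparison, all signals in the bracket are the natural common denominator. This stands. A reader might infer that the planned test is biased by the denominator. It is not, and no formal test between brackets is specified. What remains is the informal contrast that bears on Section 3, and the AcQMap region comparison.

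Second, the abnormal proportion at long cycle length is already to be reported by baseline amplitude, so differences in b will be visible. This also stands, but rescaling by (1-b) recovers q only if no signal reverts.

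Third, Section 9.1 does not say in so many words that already abnormal signals are counted, and the control-group denominator is left open. That is fair. The plain reading is all signals, and no section restricts it.

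Fourth, the all-signals proportion answers a legitimate question: how much of the tissue in a bracket becomes abnormal. That stands too, and nothing in the documents requires it to be demoted.

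Fifth, this is a secondary outcome in an exploratory study, and the Section 3 hypothesis also rests on conduction velocity, which this denominator does not affect. That limits the consequence but does not remove the point.

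**Conclusion.** The point holds as a limit on comparability. As planned, the morphology figures scale with (1-b), so they do not compare rate-sensitivity between brackets or regions with different baseline fractionation. For all participants, the reported quantities also cannot separate conversions from reversions.

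The size is unknown. The 18% versus 12% illustration rests on assumed rates (q = 20%, b = 10% and 40%) and on no reversion. It is not a prediction of what the study will report. If b turns out similar across brackets, the distortion is small.

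Two further inferences go beyond the documents. One is that intermediate-voltage tissue will look less rate-sensitive than preserved tissue. That follows only if its conversion risk is not high enough to offset the (1-b) factor, and the study's own hypothesis is of a greater response there. The other is that the same direction applies to low voltage. Section 3 reports fractionation in intermediate areas only, gives no rate, and does not tie it to the study's definition of abnormal. For the AcQMap regions the documents give no baseline rate either, so dilution there is a possibility only.

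**What to change.** In Sections 9.1 and 9.3, for all participants and by voltage bracket:

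- Add, as the measure for comparing brackets or regions, the number of signals converting to abnormal divided by the number classified normal at long cycle length.
- Report the paired 2x2 table (normal or abnormal at long by normal or abnormal at short cycle length), including changes from abnormal to normal.
- Use the same at-risk denominator for the control-group proportion and for the AcQMap region comparison, and state it there.
- Keep the all-signals proportions already planned alongside.

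The same points are already to be classified at both cycle lengths, so no new data or procedures are needed, only analysis text. The cost is precision: brackets with heavy baseline fractionation contribute fewer signals and have wider intervals. In the illustration with b = 40%, 180 of 300 signals remain in the denominator. Fixing the denominator before analysis also avoids choosing it after the results are seen. How the test handles the pairing and the clustering of points within patients is a separate matter that this change does not settle.

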The HD grid catheter is still a traditional "point by point" mapping system whereby small areas of the atrium are examined in sequence. Non-contact dipole density mapping facilitated by the AcQMap system from Acutus Medical allows real-time visualisation of whole chamber activation during AF and reveals complex propagation patterns. These patterns are highly variable between patients and their detailed analysis may identify important patterns related to the underlying electrophysiological substrate that may further our understanding of AF mechanisms and help guide effective ablation strategies.

This study therefore aims to conduct detailed EAVM using the Abbott HD grid catheter in 5 control patients undergoing ablation of left sided accessory pathways who are thought to have normal atria in order to define normal voltage amplitude and the response to changing activation rate. Detailed EAVM will then be performed in patients undergoing catheter ablation for AF in order to evaluate atrial properties at both long and short pacing cycle lengths. In 2 separate subgroups, the orthogonal HD grid mapping will be compared to either AcQMap propagation patterns or to a conventional bipolar ablation catheter with contact force. It is hypothesised that regions of intermediate voltage will demonstrate exaggerated slowing in conduction velocity and broadening of electrograms with shortening cycle length compared to regions of preserved amplitude, which will correlate with regions of slow and irregular propagation patterns during atrial fibrillation and late gadolinium enhancement on cardiac MRI. Furthermore, EAVM using the HD grid catheter will reveal higher mean electrogram amplitude compared to bipolar mapping with a lower surface area identified as low voltage (<0.5mV). The improved mapping resolution provided by the HD wave solution and HD grid catheter alongside use of varying activation times will facilitate greater understanding of the variable and patient specific AF substrate involved in AF maintenance. It is anticipated that combining this with non-invasive assessment of fibrosis distribution through cardiac MRI and AF propagation patterns visualised by panoramic mapping will provide pilot data with the potential to identify sub-groups of AF phenotypes. This data can then be applied to larger multi-centre studies of substrate mapping to better characterise the arrhythmic substrate and develop patient specific ablation strategies.

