7.7. Study visit (excluding control group)

As part of standard care, a 12 lead ECG will be performed for all patients following arrival on the day of their procedure. In line with standard practice in this institution all procedures will be undertaken under general anaesthesia.

Venous access, trans-septal puncture and placement of standard electrophysiology catheters will be undertaken as per standard clinical care. Anticoagulation will be administered following trans-septal puncture in line with standard protocols.

Please see appendix A for detailed study flow chart.

All patients

All study patients will undergo electroanatomical voltage mapping (EAVM) using the Abbott Advisor HD Grid (SE) mapping catheter using the orthogonal wave setting (HD wave solution) in the same manner as described above. If in AF at the start of the procedure direct current cardioversion (DCCV) will be used to restore sinus rhythm. This can be repeated at the discretion of the operator if initially unsuccessful (including internal cardioversion if necessary). If unsuccessful then the patient will no longer be included in the study and the procedure should continue according to standard clinical care.

Mapping will then be undertaken during bipolar pacing from the mid point of the coronary sinus catheter at a cycle length of 800ms for 4 beats followed by a single extrastimulus with coupling interval of 300ms (or the shortest captured cycle length if longer). Atrial geometry can be acquired concurrently. Care must be taken to keep the catheter in each position to record all 5 cycles before moving to acquire new points aiming for a minimum of 300 points in total with full and equal covering of the atrial surface. Interpolation threshold should be set to 7mm with points filtered to within 5mm of the surface anatomy (interior and exterior projection). Initial map collection should be specified as a CFAE map set to collect points with the catheter stationary for 5 seconds. Subsequent analyses offline will use the Precision turbomap feature to adjust the data displayed. Ablation and the rest of the procedure can then be performed according to standard clinical practice.

Post procedure care including subsequent discharge will continue in line with standard clinical practice.

Subgroup undergoing contact force guided mapping

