9.2. The Number of Participants

The total number of participants will be 35; 30 with AF and 5 controls. Previous studies have revealed the presence of low voltage areas (<0.5mV) in approximately 35% of patients with persistent AF undergoing catheter ablation,(7) and in the one previous prospective study of patients without low voltage areas, intermediate amplitude regions were observed in 43%.(9) Our hypothesis is that conduction properties, and thus electrogram morphology will become abnormal at shorter cycle length. A sample of 35 is consistent with previous mechanistic exploratory studies and should include enough patients with regions of voltage amplitude <1.1mV according to prior results outlined above and allow comparisons between each cycle length. As this is an exploratory study we are not evaluating a specific intervention, formal power calculations have limited usefulness.

The control group will consist of 5 patients with presumed normal atria. Although this is a small number, a high number of points will be collected to allow good distribution of results. By analysing the combined total electrogram recordings and excluding patients with any risk factors for abnormal atrial substrate then this sample should provide adequate estimation of normal values.

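### The long-versus-short morphology comparison uses an independent-samples chi-square on pooled electrograms, although the points are paired and clustered within patients, and no test compares the change between voltage brackets

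*Combined protocol and SAP*

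**What the plan says.** - Section 4 defines the morphology outcome within a point, by voltage bracket: "A change in electrogram morphology from normal to abnormal" between long and short pacing cycle length.
- Section 9.1 expresses it as a proportion of signals in each amplitude bracket and names one test: "Statistical comparisons using the chi-square tests of 2 proportions will be made to look for significant differences at long and short cycle length".
- Section 9.3 (all participants) has each point classified at the long cycle length. It continues: "The same sampling points will then be analysed at short cycle length and classified in the same way". The proportions normal and abnormal "will be calculated for the full sample set and according to baseline electrogram amplitude".
- Section 7.7 sets the number of points per patient: "aiming for a minimum of 300 points in total with full and equal covering of the atrial surface". Section 7.9 keeps incomplete maps when a procedure departs from protocol out of clinical necessity: "any data collected up to that point will be analysed".
- Section 9.2 gives the long-versus-short hypothesis: "Our hypothesis is that conduction properties, and thus electrogram morphology will become abnormal at shorter cycle length".
- Section 3 predicts a difference between brackets, with intermediate-voltage regions showing "exaggerated slowing in conduction velocity and broadening of electrograms with shortening cycle length compared to regions of preserved amplitude".

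The plan gives no paired test, per-patient summary, GEE, mixed model or cluster-robust variance for this outcome.

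**The concern.** The chi-square test of two proportions needs two separate samples and independent observations within each. Neither condition holds.

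- **Pairing.** The two proportions come from the same points, so they are positively correlated. The test ignores this and overstates the variance of their difference.
- **Clustering.** About 30 × 300 = 9,000 points come from 30 AF patients. If patients differ in how strongly their electrograms respond to the short cycle length, the effective sample is nearer 30 than 9,000, and the test understates the variance. Because incomplete maps are kept, patients also carry unequal weight in a pooled proportion.

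The two errors act in opposite directions, and their balance cannot be known before the data are seen. A p-value from this test therefore has an unknown error rate.

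There is also a gap. Separate tests within each bracket cannot show that one bracket responds more than another, which is the pattern section 3 predicts.

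**Working it through.** **No figure to reproduce.** Section 9.2 gives no power, alpha, effect size or variance. Alpha is taken as 5% two-sided, and every correlation and SD below is an assumption.

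**1. Pairing on a fixed example.** Take 9,000 points, 10% abnormal at long and 11% at short cycle length (900 and 990). The unpaired statistic is 0.01² / (2 × 0.105 × 0.895 / 9,000) = 4.79, p = 0.029, however the points pair up. McNemar's statistic is (difference in discordant counts)² / (their sum):

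| Discordant points (abnormal→normal, normal→abnormal) | McNemar | p |
|---|---|---|
| 90, 180 | 90²/270 = 30.0 | 0.00000004 |
| 300, 390 | 90²/690 = 11.7 | 0.0006 |
| 800, 890 | 90²/1,690 = 4.79 | 0.029 |

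The named test cannot tell these datasets apart.

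**2. Both errors in one formula.** Let *m* be the points per patient in a bracket, *p* the proportion abnormal, ρ the correlation between a point's two classifications, and τ the SD across patients of the true change in proportion. True variance divided by the variance the chi-square assumes is approximately

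R = (1 − ρ) + (m − 1)τ² / [2p(1 − p)],

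and the true level of the nominal 5% test is about 2 × [1 − Φ(1.96/√R)]. With m = 100 and p = 0.20, 2p(1 − p) = 0.32.

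- τ = 0: ρ = 0.4 gives R = 0.6, level 1.1%; ρ = 0.5 gives R = 0.5, level 0.6%.
- ρ = 0.4, τ = 3 percentage points: R = 0.6 + 99 × 0.0009/0.32 = 0.88, level 3.7%.
- ρ = 0.4, τ = 5 points: R = 0.6 + 99 × 0.0025/0.32 = 1.37, level 9.4%.
- ρ = 0.4, τ = 8 points: R = 0.6 + 99 × 0.0064/0.32 = 2.58, level 22%.

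At ρ = 0.4 the errors cancel only where τ = √(0.4 × 0.32/99) = 3.6 points.

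**3. Simulation of the null.** 30 patients × 100 points, 20% abnormal at both cycle lengths, patient intercept SD 1 logit, 2,500 runs per cell. A point SD of 2 or 3 logits gives ρ of about 0.4 or 0.5. The columns are the SD across patients of the cycle-length effect, in logits. At point SD 2, the values 0.3, 0.5 and 0.8 correspond to τ of about 3, 5 and 8 percentage points.

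| Test | 0 | 0.3 | 0.5 | 0.8 |
|---|---|---|---|---|
| Chi-square, point SD 2 | 1.3% | 4.3% | 9.7% | 22.5% |
| Chi-square, point SD 3 | 0.6% | 1.5% | 4.7% | 13.0% |
| Chi-square, no point effect | 4.2% | 11.9% | 22.4% | 38.6% |
| Pooled McNemar, point SD 2 | – | 10.4% | 18.0% | 33.5% |
| Pooled McNemar, point SD 3 | – | 9.0% | 17.2% | 28.6% |

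The patient-level paired t-test rejected 4.2–5.8% across all 30-patient scenarios. It also held at 4–6% with only 10 patients, which matters because section 9.2 expects low-voltage areas in about 35% of patients with persistent AF (0.35 × 30 = 10.5).

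With 200 points per bracket and effect SD 0.3/0.5/0.8, the chi-square rejected 7%/19%/35% (point SD 2) and 3%/10%/26% (point SD 3).

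**4. Controls.** If the chi-square were also applied to 5 controls × 300 points at 10% abnormal, it would reject 4–38% for effect SD 0.3–0.8. The patient-level test rejects 3–5%.

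**5. Between-bracket comparison.** A within-patient paired comparison of two brackets with equal true change (20% to 25% in both) rejected 4–6%.

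**The case against.** - **The sentence in section 9.1 is ambiguous.** It could mean comparing brackets at each cycle length. Pairing would then largely drop out and a between-bracket test would exist. Section 9.2 speaks of comparing cycle lengths, which favours the other reading. On either reading the clustering remains and the difference in change is untested.
- **The section 3 prediction concerns conduction velocity and electrogram broadening, not the binary class.** That is fair. But section 4 splits the binary outcome by the same brackets, so the comparison is a natural one to specify.
- **The reference to the whole sample in section 9.3 may mean only all amplitudes together.** It may. Pooling over patients then follows from section 9.1, where the unit is the signal.
- **The percentages are driven by assumptions, and some cells are close to 5%.** True. They show that the error can go either way, not what it will be. The mismatch between test and data does not depend on them.
- **Section 9.3 only records changes in the controls.** True, so the control figures are conditional on the test being used there.
- **The study is exploratory and this outcome is secondary.** This limits the consequence. But the plan still intends to look for significance, and section 3 wants the data to inform larger studies.

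**Conclusion.** The concern holds. The named test contradicts the plan's own description of the data, and no other method is given for this outcome. Under the assumed 30 × 100 setting with paired points, its true level at a nominal 5% runs from 0.6% to 23%; with more points per bracket or no point-level correlation it goes higher. The direction cannot be fixed in advance, so it would be wrong to say that the p-values are always too small. The missing test of the difference in change between brackets is a second, separable gap. This should be fixed, but it does not threaten the primary outcome, which does not use this test.

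**What to change.** Reword sections 9.1 and 9.3:

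1. For each patient and bracket, calculate percent abnormal at short minus percent abnormal at long cycle length, and test the mean change across patients with a paired patient-level test. This net change matches the proportions section 9.3 already calculates. Because section 4 defines the outcome as normal to abnormal, also report per patient the share of baseline-normal points that became abnormal, and the reversals.
2. Compare the change between the intermediate and normal brackets within patients who have points in both.
3. Alternatively, use a logistic GEE clustered by patient, with an independence working correlation, a cycle-length by bracket interaction and small-sample standard errors. A mixed model would need a patient-level cycle-length slope.
4. State which is used. The first averages over patients in percentage points, the second over electrograms as an odds ratio, and the interaction can differ by scale. The odds ratio that takes 20% to 25% is (0.25/0.75)/(0.20/0.80) = 1.33, and it takes 10% to 12.9% and 40% to 47.1%.
5. Do not use McNemar's test on pooled points.
6. Report the numbers of patients and points in each bracket, and describe the 5 controls patient by patient.

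**Cost:** a wording change and slightly more analysis, with no new data or procedures. Intervals will be wider than the naive ones where patient variation dominates (R above 1) and narrower where pairing dominates. Patients without points in both brackets drop out of the patient-level between-bracket comparison.
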